10. DIRECT ACCESS TO SOURCE DATA/DOCUMENTATION

Patients will be identified on study records by a unique Patient identification number and on source documents by name and date of birth. No personal identifier will be used in any publication or communication used to patient this research study. The subject identification number will be used if it becomes necessary to identify data specific to a single patient.

The local IRB, FDA, the monitors, auditors and personnel authorized by the Investigator/Sponsor are eligible to review the medical and research records related to this study as part of their responsibility to protect human patients in clinical research. They will be given direct access to source data and documentation (e.g., medical charts/records, printouts etc.) for source data verification, provided that patient confidentiality is maintained in accordance with local requirements. Access to electronic medical records may be governed by institution policy. The Investigator will be required to ensure access while remaining compliant with institutional requirements.

11. QUALITY CONTROL AND QUALITY ASSURANCE

11.1. MONITORING REQUIREMENTS

The Investigator/Sponsor should be aware that the study site and patient records may be inspected by the FDA or other regional regulatory authority.

11.2. MODIFICATION OF PROTOCOL

The Investigator/Sponsor will not modify or alter this protocol without first obtaining the concurrence of the Sponsor. Approval by the Investigator/Sponsor's IRB must also be obtained prior to implementation of the change, with two exceptions:

1. When necessary to eliminate apparent immediate hazard to the patient; or
2. When the modification does not involve the patient's participation in the trial.

An amendment may also require modification of the informed consent form.

11.3. REPORTING PROTOCOL DEVIATIONS

The Investigator/Sponsor is obligated to follow the protocol without departure from the requirements written in the protocol. The Investigator/Sponsor also has the right to discontinue the patient for protocol violations. The IRB may also have to be contacted if safety to the patient or if the scientific soundness of the study is involved.

11.3.1. Major Protocol Deviation or Violation

A major protocol deviation or violation is a deviation from the IRB approved protocol that may affect the patient's rights, safety, or well-being and/or the completeness, accuracy and reliability of the study data. Examples of this include:

- Failure to obtain informed consent prior to initiation of study-related procedures
- A research patient does not meet the protocol's eligibility criteria but was enrolled
- A research patient received the wrong treatment or incorrect dose.
- A research patient met withdrawal criteria during the study but was not withdrawn.
- A research patient received a prohibited concomitant medication.
- Failure to treat research patients per protocol procedures that specifically relate to primary outcome measures.

- Changing the protocol without prior IRB approval.
- Multiple minor violations of the same nature after multiple warnings.

11.3.2. Minor Protocol Deviation or Violation

A minor protocol deviation is any change, divergence, or departure from the study design or procedures of a research protocol that has not been approved by the IRB and which does NOT have a major impact on the patient's rights, safety or well-being, or the completeness, accuracy and reliability of the study data. Examples of this include:

- Follow-up visits that occurred outside the protocol required time frame because of the patient's schedule.
- Blood samples obtained at times close to but not precisely at the time points specified in the protocol.

12. ETHICS AND REGULATORY REQUIREMENTS

This study is to be conducted in accordance with the specifications of this protocol and in accordance with principles consistent with Declaration of Helsinki, GCP, 21 CFR, ICH E6, HIPAA regulations in 45 CFR Part 164 (US only), and the Belmont Principles of respect for persons, beneficence, and justice. No protocol changes will be implemented without the prior review and approval of the IRB, except when the modification does not involve the patient's participation in the trial or where it may be necessary to eliminate an immediate hazard to a research patient. In the latter case, the change will be reported to the IRB as soon as possible, according to IRB regulations.

Additionally, the study product used in this study is manufactured, handled and stored in accordance with applicable GMP. The study product provided for this study will be used only in accordance with this protocol.

12.1. INSTITUTIONAL REVIEW BOARD/INDEPENDENT ETHICS COMMITTEE (IRB/IEC)

The Investigator/Sponsor will provide the Institutional Review Board/Independent Ethics Committee (IRB/IEC) with all appropriate materials as required by their IRB/IEC, including but not limited to the clinical study protocol, informed consent form, and any advertising materials. The study will not be initiated until the IRB/IEC provides written approval of the aforementioned document. The Investigator will not participate in the decision. If the Investigator is an IRB or IEC member, documentation must be provided indicating recusal from the approval process. Appropriate reports on the progress of this study by the Investigator will be made to the IRB/IEC as required by local and applicable government regulations. The Investigator is required to maintain an accurate and complete record of all written correspondence to and received from the IRB/IEC.

No changes from the final approved protocol will be initiated without the IRB/IEC's prior written approval or favorable opinion of a written amendment, except when necessary to eliminate immediate hazards to the patients or when the modification does not involve the patient's participation in the trial.

12.2. INVESTIGATOR'S RESPONSIBILITIES

The Investigators are responsible for performing the study in full accordance with the protocol and the current revision of the Declaration of Helsinki, the Good Clinical Practice: Consolidated Guideline, approved by the ICH, and any applicable national and local laws and regulations. Information regarding to the study center participating in this study that cannot comply with these standards will be documented.

12.3. PATIENT INFORMED CONSENT REQUIREMENTS

All patients participating in this study will be given to by the Investigator and/or designee, written and oral information about the study in a language understandable by the patient. Written informed consent will be obtained from each patient prior any procedures or assessments that would not otherwise be required for the care of the patient are done and after the aims, methods, anticipated benefits, potential hazards, and insurance arrangements in force are explained and the patient has been given sufficient time to ask questions and consider participation in the study. It will also be explained to the patients that they are free to refuse entry into the study and free to withdraw from the study at any time without prejudice to future treatment. It is permissible for a third person (e.g., a family member) to be present during the explanation of the study.

The written Informed Consent Form (ICF) will be in compliance with CFR 21 Part 50.27 and GCP guidelines. A copy of the ICF to be used will be submitted by the Investigator/Sponsor to the IRB/IEC for review and approval prior to the start of the study. The original signed ICF is retained in the patient's study records, and a copy is provided to the patient. A second copy may be filed in the patient's medical record, if allowed by institutional policy.

13. DATA HANDLING AND RECORD KEEPING

13.1. RECORDING AND COLLECTION OF DATA

The primary source document for this study will be the patient's medical record. If separate research records are maintained by the Investigator(s), the medical record and the research records will be considered the source documents for the purposes of auditing the study.

The Investigator will maintain a confidential list of study patients that will include each patient's study number, name, date of birth, and unique hospital identification number if applicable. A notation will be made in the patient's case history/medical chart that he/she is participating in a clinical study and has provided a signed and dated ICF as well as a release for protected health information as required by local policies. The Investigator must also maintain a separate screening log of all the patients screened for participation in the study; it should include gender, age, eligibility status, reason for ineligibility, if applicable; and study allocated patient number, if applicable.

13.2. ARCHIVING

All study documentation at the Investigator site will be archived in accordance with ICH GCP E6 and the Investigator/Sponsor's quality standards and SOPs.

The Investigator will maintain all research records, reports, and case history reports for a period of two (2) years after regulatory approval of the investigational product. If no application is filed or if the application is not approved, records must be maintained for two (2) years after all investigations have been completed, terminated or discontinued and the FDA has been notified.

These documents should be retained for a longer period however, if required by the applicable regulatory requirements (as per GCP 5.5.11).

Study records are subject to inspection by applicable health and regulatory agencies at any time.

Records to be retained by the Investigator include, but are not restricted to:

- Source data and the primary records upon which they are based (e.g., patient's progress notes, AE data, test results, and any other diagnostic procedures required to evaluate the progress of the study)
- Signed protocols and protocol amendments
- Laboratory results, ranges, and certifications
- IP and accountability records
- Study personnel signature log

- Monitoring logs
- Investigator and sub-investigator CVs
- Signed informed consent and protected health information consent forms
- Patient screening
- SAE reports
- IRB approval and re-approval letters
- Completed quality of life questionnaire
- Other documents pertaining to the conduct of the study

These documents must be maintained and kept on file by the Investigator so that the conduct of the study can be fully documented and monitored.

Study records are subject to inspection by applicable health and regulatory agencies at any time.

16. APPENDIX

16.1. APPENDIX 1: EQ-5D-5L QUESTIONNAIRE

Under each heading, please tick the ONE box that best describes your health TODAY.

MOBILITY

I have no problems in walking about	
I have slight problems in walking about	
I have moderate problems in walking about	
I have severe problems in walking about	
I am unable to walk about	

SELF-CARE

I have no problems washing or dressing myself	
I have slight problems washing or dressing myself	
I have moderate problems washing or dressing myself	
I have severe problems washing or dressing myself	
I am unable to wash or dress myself	

USUAL ACTIVITIES (e.g. work, study, housework, family or leisure activities)

I have no problems doing my usual activities	
I have slight problems doing my usual activities	
I have moderate problems doing my usual activities	
I have severe problems doing my usual activities	
I am unable to do my usual activities	

[figure not shown]
PAIN / DISCOMFORT

I have no pain or discomfort	
I have slight pain or discomfort	
I have moderate pain or discomfort	
I have severe pain or discomfort	
I have extreme pain or discomfort	

ANXIETY / DEPRESSION

I am not anxious or depressed	
I am slightly anxious or depressed	
I am moderately anxious or depressed	
I am severely anxious or depressed	
I am extremely anxious or depressed	

- We would like to know how good or bad your health is TODAY.
- This scale is numbered from 0 to 100.
- 100 means the best health you can imagine.
0 means the worst health you can imagine.
- Mark an X on the scale to indicate how your health is TODAY.
- Now, please write the number you marked on the scale in the box below.

YOUR HEALTH TODAY = The best health
you can imagineThe worst health
you can imagine

16.2. APPENDIX 2: TOXICITY GRADING SCALE FOR HEALTHY ADULT AND ADOLESCENT VOLUNTEERS ENROLLED IN PREVENTIVE VACCINE CLINICAL TRIALS

For complete detailed information please refer to the link below:

<https://www.fda.gov/media/73679/download>

16.3. APPENDIX 3: ASSESSMENT OF COVID-19-RELATED SYMPTOMS (PATIENT DIARY)

Assessment of COVID-19-related symptoms

Subject Number: _____

Date and time of Assessment: _____

1. What was the severity of your cough at its worst over the last 24 hours?	 None  Mild  Moderate  Severe
2. What was the severity of your sore throat at its worst over the last 24 hours?	 None  Mild  Moderate  Severe
3. What was the severity of your stuffy or runny nose at its worst over the last 24 hours?	 None  Mild  Moderate  Severe
4. What was the severity of your shortness of breath (difficulty breathing) at its worst over the last 24 hours?	 None  Mild  Moderate  Severe
5. What was the severity of your feeling of tightness of chest at its worst over the last 24 hours?	 None  Mild  Moderate  Severe
6. What was the severity of your feeling of fast heartbeat at its worst over the last 24 hours?	 None  Mild  Moderate  Severe
7. What was the severity of your low energy or tiredness at its worst over the last 24 hours?	 None  Mild  Moderate  Severe
8. What was the severity of your muscle cramps at its worst over the last 24 hours?	 None  Mild  Moderate  Severe
9. What was the severity of your joint pain at its worst over the last 24 hours?	 None  Mild  Moderate  Severe
10. What was the severity of your chills or shivering at its worst over the last 24 hours?	 None  Mild  Moderate  Severe
11. What was the severity of your feeling hot or feverish at its worst over the last 24 hours?	 None  Mild  Moderate  Severe
12. What was the severity of your difficulty in concentration (brain fog) at its worst over the last 24 hours?	 None  Mild  Moderate  Severe
13. What was the severity of your sleep disturbance (insomnia) at its worst over the last 24 hours?	 None  Mild  Moderate  Severe
14. What was the severity of your headache at its worst over the last 24 hours?	 None  Mild  Moderate  Severe
15. What was the severity of your dizziness at its worst over the last 24 hours?	 None  Mild  Moderate  Severe
16. What was the severity of your anxiety at its worst over the last 24 hours?	 None  Mild  Moderate  Severe
17. What was the severity of your feeling of tingling or numbness in at its worst over the last 24 hours?	 None  Mild  Moderate  Severe
18. What was the severity of your nausea (feeling like you wanted to throw up) at its worst over the last 24 hours?	 None  Mild  Moderate  Severe
19. How many times did you vomit (throw up) in the last 24 hours?*	 I did not vomit at all  one or two times  three or four times  five or more times
20. How many times did you have diarrhea (loose or watery stools) in the last 24 hours?*	 I did not have diarrhea at all  one or two times  three or four times  five or more times
21. Rate your sense of smell in the last 24 hours	 My sense of smell is THE SAME AS usual  My sense of smell is LESS THAN usual  I have NO sense of smell
22. Rate your sense of taste in the last 24 hours	 My sense of taste is THE SAME AS usual  My sense of taste is LESS THAN usual  I have NO sense of taste

*The response options shown for items 19 and 20 are intended only for use with a 24-hour recall period.

## 1 Statistical Changes from Study Protocol

The statistical analysis methods will follow study protocol version amendment 1.0 (11-MAY-2021, exceptions and clarifications are described below:

### 1.1 Visit Adjustment

Visit 6 is End of Treatment (EOT) Visit, Treatment Discontinuation Visit or Early Withdrawal Visit at/before EOT. Data of visit 6 not in its visit window will be shifted to corresponding scheduled visit for analysis as in table below (marked ‘\*’). Visit name will be presented as ‘Adjusted Visit’ for the visits reallocated to its original scheduled visit or the next visit after preceding scheduled visit.

	Visit 6 to Visit 3~6
COVID-19-Related Symptoms	*
Clinical Status - NIAID 8-Point Clinical Progression Outcomes Scale	*
Laboratory Examination	*
Vital Signs, Pulse Oxygen Saturation (SpO2) and COVID-19-Related Clinical Signs	*

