6. STUDY TREATMENT

6.1. STUDY TREATMENT ADMINISTRATION

6.1.1. Investigational Drug Product Description

For this study, the investigational product is CX-4945 that will be assigned to the subjects randomized to treatment Arm A.

Refer to the Investigator's Brochure for more information.

All patients enrolled in the study (Arm A and Arm B) may be treated with SOC/best supportive care as per the Investigator's discretion and in accordance with the site standard clinical practice. The patients randomized to treatment Arm A will receive SOC/best supportive care therapy in combination with CX-4945. The patients randomized to the control Arm B will receive SOC/best supportive care alone.

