7.3. PATIENT DISCONTINUATION FROM STUDY TREATMENT

Patients may withdraw from treatment at any time at their own request, or they may be withdrawn at any time at the discretion of the investigator/sponsor for safety or behavioral reasons, or the inability of the patient to comply with the protocol-required schedule of study visits or procedures at a given investigator site.

All patients who discontinued from study treatment but maintain consent, should remain in the study through the end of the study period for all important safety and anti-viral activity assessments.

Investigators considering patient withdrawal from study treatment should contact the medical monitor prior to such discontinuation. Patients who have study treatment discontinued will continue to be followed, per protocol, whenever possible. If visits to the site are not possible,

subjects can be followed via telehealth or other approaches (telephone calls, e-mails, and texts to ascertain vital status in all patients.

Patients who have study treatment discontinued due to a serious adverse event will be followed until study completion, resolution or stabilization of the event (whichever occurs later).

Reasons for withdrawal of study treatment may include:

- Patient refused further treatment
- Pregnancy
- Unacceptable toxicity
- Significant study therapy non-compliance
- If any clinical adverse event (AE), laboratory abnormality, or other medical condition or situation occurs such that continued participation in the study would not be in the best interest of the participant
- Disease progression which requires discontinuation of the study intervention
- If the participant meets an exclusion criterion (either newly developed or not previously recognized) that precludes further study participation

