## (4) For Visit Name (in Tables and Figures) and Visit Code (in Subject Data Listing):

Visit No.	Visit Description	Visit Day	Visit Name	Visit Code
1	Screening Visit	-7 ~ -1	Visit 1 (Screening)	V01
2	Treatment Visit (Day 1)	1	Visit 2 (Day 1)	V02D01T
3	Treatment Visit (Day 4)	4 ± 1	Visit 3 (Day 4)	V03D04T
4	Treatment Visit (Day 8)	8 ± 1	Visit 4 (Day 8)	V04D08T
5	Treatment Visit (Day 11)	11 ± 1	Visit 5 (Day 11)	V05D11T
6	End of Treatment (EOT)Visit (Day 14)	14 ± 1	Visit 6 (Day 14, EOT)	V06D14E
7	Follow-up 1 Visit (Day 28)	28 ± 3	Visit 7 (Day 28, F1)	V07D28F
8	Follow-up 2 Visit (Day 45)	45 ± 3	Visit 8 (Day 45, F2)	V08D45F
9	Follow-up 3 Visit (Day 60)	60 ± 3	Visit 9 (Day 60, F3)	V09D60F
	Unscheduled Visit	-	-	UV

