## 14.2.3 Nasopharyngeal Swab RT-PCR Result and SARS-CoV-2 Viral Load

### 14.2.3.1 SARS-CoV-2 Viral Clearance and Viral Load [copies/µL]

Population: Intent-to-Treat Population / Per-Protocol Population

Characteristics	Treatment Group	Difference	P-value
--Repeat Population: <See populations above>			
. Repeat Visit:			
Visit 1 (Screening), Baseline, Visit 4 (Day 8), Visit 6 (Day 14, EOT), Visit 7 (Day 28, F1), LOCF			
N (Missing)	XXX (XXX)		
Negative	XXX (XXX.X%)		
Positive	XXX (XXX.X%)		
N (Missing)	XXX (XXX)		0.XXXX
Mean (SD)	XXX (XXX)		
Median (IQR)	XXX (XXX)		
Q1~Q3	XXX~XXX		
Min~Max	XXX~XXX		
Repeat [Baseline to Visit] except Visit 1 (Screening) and Baseline			C/F
N (Missing)	XXX (XXX)	0.XXXX	
Positive to Negative#	XXX (XX.X%)		
Positive to Positive	XXX (XX.X%)		
Diff. between groups	§C - §S		
Difference (#)	XXX%		
95% CI (#)	XXX% ~XXX%a		
Repeat [Visit - Baseline] except Visit 1 (Screening) and Baseline			TW
N (Missing)	XXX (XXX)	0.XXXX	
Mean (SD)	XXX (XXX)		
Median (IQR)	XXX (XXX)		
Q1~Q3	XXX~XXX		
Min~Max	XXX~XXX		
For W, normality is not applied			
Groups Diff	§C - §S		
Median (Asymptotic SE)	XXX		
95% CI (HL)	XXX~XXX		
For T, normality is applied			
Groups Diff	§C - §S		
Mean (SD)	XXX (XXX)		
95% CI	XXX~XXX		

a denotes CI using normal approximation for binomial proportion of #  
 Viral Load > 25,000.00 copies/µL is estimated as 25,000.00 copies/µL.  
 Baseline is Visit 2 (Day 1) data, or is Visit 1 if Visit 2 (Day 1) is null

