## 14.2.4 Clinical Status - NIAID 8-Point Clinical Progression Outcomes Scale

### 14.2.4.1 Clinical Status - NIAID 8-Point Clinical Progression Outcomes Scale

Population: Intent-to-Treat Population / Per-Protocol Population

Characteristics	Treatment Group	P-value
--Repeat Population: <See populations above>		
N	XXX	
Subjects with any below [Event#:Subj#]	XXX : XXX (XXX.X%)	
~ Death (NIAID item 1)	XXX : XXX (XXX.X%)	
~ Respiratory Failure (NIAID item 2~3 or from AE)	XXX : XXX (XXX.X%)	
~ Hospitalized (NIAID item 2~6)	XXX : XXX (XXX.X%)	
. Repeat Visit: No 'Visit 1 (Screening)' for IL-6: Visit 1 (Screening), Baseline, Adjusted Visit 3 (Day 4), Adjusted Visit 4 (Day 8), Adjusted Visit 5 (Day 11), Adjusted Visit 6 (Day 14, EOT), Visit 7 (Day 28, F1), Visit 8 (Day 45, F2), LOCF		
N (Missing)	XXX (XXX)	0.XXXX
Item 1	XXX (XXX.X%)	
Item 2	XXX (XXX.X%)	
...	...	
Item 8	XXX (XXX.X%)	
Repeat [Baseline to Visit] except Visit 1 (Screening), Baseline		
N (Missing)	XXX (XXX)	C/F
Improvement (Item 7 to Item 8)	XXX (XX.X%)	0.X
Progression (Item 7 to Item 1~6)	XXX (XX.X%)	XX
		X

Respiratory failure required mechanical ventilation, oxygen delivered by high-flow nasal cannula, ESMO; shock or multi-organ dysfunction/failure

For NIAID 8-Point Clinical Progression Outcomes Scale:

Item 1 - Death

Item 2~3 - Hospitalized, respiratory failure

Item 4~6 - Hospitalized, non-respiratory failure

Item 7 - Not hospitalized, limitation on activities and/or requiring home oxygen

Item 8 - Not hospitalized, no limitations on activities

Refer to [Instructions and Abbreviations] of title pages for further definition

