## 14.2.5 EQ-5D-5L

### 14.2.5.1 EQ-5D-5L

Population: Intent-to-Treat Population / Per-Protocol Population

Characteristics	Treatment Group	Difference	P-value
--Repeat Population: <See populations above>			

. Repeat Visit:

Visit 2 (Day 1), Visit 4 (Day 8), Visit 6 (Day 14, EOT), Visit 7 (Day 28, F1), LOCF

. Repeat Variable:

*Total score of Q1~Q5, Imaginable Health Status*

N (Missing)	XXX (XXX)	TW (Visit 2 (Day 1)) 0.XXXX
Mean (SD)	XXX (XXX)	
Median (IQR)	XXX (XXX)	
Q1~Q3	XXX~XXX	
Min~Max	XXX~XXX	

*For Imaginable Health Status only*

≥ 90	XXX (XXX.X%)
< 90	XXX (XXX.X%)

Repeat [Visit - Visit 2 (Day 1)] except Visit 2 (Day 1)

N (Missing)	XXX (XXX)	TW 0.XXXX
N (Missing)	XXX (XXX)	
Mean (SD)	XXX (XXX)	
Median (IQR)	XXX (XXX)	
Q1~Q3	XXX~XXX	
Min~Max	XXX~XXX	

For W, normality is not applied

Groups Diff	§C - §S
Median (Asymptotic SE)	XXX
95% CI (HL)	XXX~XXX

For T, normality is applied

Groups Diff	§C - §S
Mean (SD)	XXX (XXX)
95% CI	XXX~XXX

Q1. Mobility, Q2. Self-Care, Q3. Usual Activities, Q4. Pain/Discomfort, Q5. Anxiety/Depression

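### RT-PCR, viral load and EQ-5D-5L taken at an early discontinuation or withdrawal visit would be shown and tested in the row labelled Day 14

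*SAP*

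**What the plan says.** SAP 1.1 gives Visit 6 three meanings: "Visit 6 is End of Treatment (EOT) Visit, Treatment Discontinuation Visit or Early Withdrawal Visit at/before EOT". It adds: "Data of visit 6 not in its visit window will be shifted to corresponding scheduled visit for analysis as in table below". The table marks four groups: COVID-19 symptoms, the NIAID 8-point scale, laboratory examinations, and vital signs with SpO2 and clinical signs. The nasopharyngeal swab and EQ-5D-5L do not appear.

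The mock tables follow the same split. Table 14.2.3.1 (RT-PCR and viral load) lists "Visit 1 (Screening), Baseline, Visit 4 (Day 8), Visit 6 (Day 14, EOT), Visit 7 (Day 28, F1), LOCF", and table 14.2.5.1 (EQ-5D-5L) lists "Visit 2 (Day 1), Visit 4 (Day 8), Visit 6 (Day 14, EOT), Visit 7 (Day 28, F1), LOCF". The NIAID table 14.2.4.1, by contrast, ends its list with "Adjusted Visit 6 (Day 14, EOT), Visit 7 (Day 28, F1), Visit 8 (Day 45, F2), LOCF". The laboratory layouts and table 14.3.8 also use adjusted visits.

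On the arms, Protocol 6.1.1 says: "The patients randomized to the control Arm B will receive SOC/best supportive care alone". On follow-up, Protocol 7.3 says that patients who stop study treatment but keep their consent "should remain in the study through the end of the study period for all important safety and anti-viral activity assessments".

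**The concern.** A patient who stops CX-4945 on Day 5, and has a swab and questionnaire at that visit, has a Visit 6 on Day 5. For the four listed groups the SAP moves those data out of the Day 14 row. For RT-PCR, viral load and EQ-5D-5L it leaves them there, and both tables plan between-group p-values and confidence intervals on change from baseline at that row.

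COVID-19 outpatients can be expected to clear virus and feel better over two weeks whatever they receive. An early value read as Day 14 therefore understates that patient's Day 14 state. Only Arm A has a study drug to stop, so this part of the error depends on tolerability and falls on one arm. With about 10 patients per arm (Protocol 9.3), one or two such values can move an estimate visibly.

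**Working it through.** The documents give no power, effect size or dropout figure, so there is no planned number to reproduce. The check is a comparison of rules, followed by an illustration of scale.

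**1. Which outputs are re-slotted**

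| Assessment | In SAP 1.1 shift list | Visit 6 label in mock table |
|---|---|---|
| NIAID scale (14.2.4.1) | yes | adjusted |
| Laboratory tests (14.3.2–14.3.6) | yes | adjusted |
| Vital signs, SpO2 (14.3.8) | yes | adjusted |
| RT-PCR, viral load (14.2.3.1) | no | unadjusted |
| EQ-5D-5L (14.2.5.1) | no | unadjusted |

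The laboratory heading does not cover the swab: in this SAP it means sections 14.3.2 to 14.3.6, and RT-PCR is section 14.2.3.

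**2. Which days are out of window**

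From the SAP visit table, Visit 3 is Days 3–5, Visit 4 Days 7–9, Visit 5 Days 10–12 and Visit 6 Days 13–15. Days 2 and 6 belong to no window. A discontinuation or withdrawal visit on Days 2–12 is thus outside the Visit 6 window, yet for these three measures it stays in the Day 14 row.

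**3. Which results depend on that row**

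- EQ-5D-5L change to Day 14 is a named secondary endpoint (Protocol 1.1 and 3), so it is affected.
- The virologic endpoints are conversion through Day 28, time to clearance, and viral load change to Day 28. Day 28 rows use Visit 7. Only the interim Day 14 rows of 14.2.3.1 are affected.
- Time to clearance and time to EQ-5D-5L improvement count days from actual dates (SAP 1.4.2), so they are not mislabelled.

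**4. Illustration for RT-PCR conversion**

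The assumptions, none from the documents except the arm size, are: 10 per arm; no drug effect; exponential clearance from Day 1; a proportion p14 of 50–80% negative by Day 14; k Arm A patients stopping on day d and swabbed then; and no real Day 14 swab used for them.

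- Daily hazard: h = −ln(1 − p14)/13, which is 0.0533 for p14 = 0.5 and 0.1238 for p14 = 0.8.
- Chance of being negative at day d: P(d) = 1 − exp(−h(d − 1)). Day 4 gives 15% to 31%; Day 6 gives 23% to 46%.
- Fall in the Arm A Day 14 proportion: (k/10) × (p14 − P(d)).

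| k | d = 4 | d = 6 |
|---|---|---|
| 2 | 7.0 to 9.8 points | 5.3 to 6.8 points |
| 3 | 10.6 to 14.7 points | 8.0 to 10.2 points |

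For example, k = 2, d = 4, p14 = 0.8 gives 0.2 × (0.80 − 0.31) = 9.8 points.

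A cruder version without the exponential form takes p14 of 40–80% and early negativity of 0–20%. With k from 1 to 3, the fall is 2 points (0.1 × (0.4 − 0.2)) to 24 points (0.3 × (0.8 − 0)).

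**5. Illustration for EQ-5D-5L**

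If the 0–100 health score rises by an assumed 10–30 points between the early visit and Day 14, the Arm A mean is low by (k/10) × gain. That is 1 point (k = 1, gain 10) to 9 points (k = 3, gain 30).

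No figure is offered for viral load. Table 14.2.3.1 reports copies/µL capped at 25,000, and the documents give no basis for a rate of decline on that scale.

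**The case against.** The omission may be deliberate. The four listed groups are those assessed at each of Visits 3 to 6, whereas swabs and EQ-5D-5L are scheduled only on Days 1, 8, 14 and 28. Visits 3 and 5 have no row for them. This explains the list but does not remove the problem: the early values stay in a row labelled Day 14. It also shows that simply adding these measures to the list would not be enough. An assessment on Days 2–6 has no row of its own. SAP 1.1 also allows reallocation to the visit following the last scheduled one, which could put a Day 5 swab in the Day 8 row and return a Day 10–12 swab to Visit 6.

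A reader might infer that the row sets early Arm A values against true Day 14 values in Arm B. The documents do not guarantee that. Early-withdrawal visits are also Visit 6 and can occur in Arm B, so the net direction is not fixed. Only the discontinuation component is one-sided.

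A reader might also infer that the SAP discards the real Day 14 assessment of a patient who stopped drug. It does not say so. Protocol 7.3 keeps such patients in follow-up, and the SAP is silent on which record is Visit 6 when both exist. The Schedule of Activities has no separate discontinuation visit and does not require a swab at one, so how often an early value would arise is unknown.

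Finally, the trial is small, unpowered and has a safety primary endpoint, and the discontinuation bias runs against the drug. If a true 6/10 in each arm became 4/10 against 6/10, Fisher's exact p would be 0.66. That stands: the harm is a distorted estimate, not a false claim of efficacy.

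**Conclusion.** The gap is plain in SAP 1.1 and repeated in tables 14.2.3.1 and 14.2.5.1. Followed as written, the rule shows and tests early RT-PCR, viral load and EQ-5D-5L values as Day 14. The one named endpoint directly affected is the Day 14 EQ-5D-5L change; the interim Day 14 RT-PCR and viral load rows are affected too. It would go too far to say that the anti-viral objective as a whole is biased, because its endpoints rest on Day 28 rows or actual dates.

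The direction, against CX-4945, holds for discontinuation visits and assumes improvement over time. The size, about 5 to 10 points on Day 14 conversion with 2 of 10 stopping on Days 4–6, is an illustration under the stated assumptions. It could be zero if no one stops early, or if no one who does is assessed at that visit. The correction is worth making because it is cheap and the arms are small.

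**What to change.** In SAP 1.1, 14.2.3.1 and 14.2.5.1, for RT-PCR, viral load and EQ-5D-5L:

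- Define the Day 14 row by study day (14 ± 1) in both arms.
- Assign an early end-of-treatment, discontinuation or withdrawal assessment to Visit 4 only if it falls in Day 8 ± 1. Otherwise keep it out of both the Day 8 and Day 14 rows. It still counts in the LOCF row and, by actual date, in the time-to-event analyses.
- Where a patient has both an early assessment and a real Day 14 assessment, use the real one for the Day 14 row.
- Label the rows as adjusted visits, as the other tables do.

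The cost is SAP wording and some programming, with no new data collection. A few Day 14 cells become missing, which the tables already report.
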